# 9.1.1.2. Visit Reminders- Telephone Contacts

Prior to each visit, subjects should be contacted and reminded of:

- The date and time of their clinic appointment.
- The requirement to fast for at least 8 hours prior to clinic visits on Day 1 (Randomization Visit), Week 26, Week 52, and unscheduled visit for initiation of glycemic rescue therapy.
- The requirement on the morning of clinic visits at Week 12, 26, and 52 to not take blinded study drug prior to coming to the clinic.
  - **Note:** Non-study medications that are not AHAs should be taken as directed by the prescribing physician.
- The requirement to bring study drugs, glucometer, hypoglycemia assessment tool(s), any collected SMBG measurements and ketone information to the clinic visit.

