# 9.2. Ketone Monitoring

Subjects will be provided with a capillary blood ketone meter and strips. It should be noted that capillary blood ketone testing is the preferred methodology for decision making, as it provides a quantitative measure of  $3\beta$ -OH butyrate which accounts for approximately 75% of the ketones (Foster 1983) and represents a more sensitive marker to detect and monitor ketonemia. On the contrary, the urine ketone test provides a qualitative assessment of aceto-acetate and appears to be less sensitive in detecting early stages of ketosis and may be overestimating the degree of ketosis during its resolution phase.

Subjects and parents/legal guardians will be counseled on various aspects of sick day management and ketone monitoring aiming at early identification of elevated ketone levels and timely intervention in order to prevent or reduce the risk of progression to ketoacidosis. In particular, subjects will receive counseling on

- Importance of monitoring ketones any time the subject is ill or does not feel well, or has any potential precipitating factors for ketone elevation or DKA;
- Recognition of signs and symptoms of ketosis and DKA;
- Management of insulin and food intake during illness and/or in presence of elevated ketone levels.

See Attachment 1, Instructions on Ketone Monitoring and Sick Day Management and Attachment 2, Suggested Algorithm for Ketone Monitoring and Findings of Elevated Ketones.

During the study, subjects will return the diary containing information on ketone measurements and if applicable, action taken by the subject to treat elevated ketone levels. Study site personnel will be required to review the diaries and enter only the data of elevated ketones (ie,  $\geq 0.6$  mmol/L) along with other pertinent information (concomitant blood glucose levels, signs/symptoms of illness, precipitating factors, etc) on a specific eCRF. In addition, upon

review of the diaries, findings of elevated ketones considered by the investigator to be adverse events should also be reported in the adverse event eCRF. In addition, any illness considered to be a precipitating factor of the ketone elevation should be reported as an adverse event, if appropriate, on the adverse event eCRF.

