# 9.2.1.1. Pre-specified Ketone Measurements During Run-in Period

Subjects will be required to measure and document in their study diary capillary blood ketones and blood glucose on a minimum of 3 days during the 2-week run-in period (to assess subject's pre-dose ketone levels and compliance with ketone management procedure). The measurements do not have to be made on 3 consecutive days.

To avoid the confounding effect of overnight fasting on ketogenesis, for the pre-specified ketone assessment procedures, the blood ketone measurements should be obtained in a non-fasting state. If non-symptomatic ketone elevations are found in the fasting state, subjects should be instructed to repeat the ketone measurement after breakfast.

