Subjects are required to enter pertinent information related to elevated ketones during illness (eg, concomitant [or closest in time] glucose levels, insulin dose and changes in insulin dose [if applicable], precipitating factors) on a subject diary and the information will be captured on a specific eCRF. Upon review of the subject's ketone measurements, the site will be required to report only the episodes of elevated ketone levels (ie,  $\geq 0.6$  mmol/L) and the pertinent information onto the specific eCRF. The concomitant illness should be reported as a separate adverse event and study drug treatment interruptions will be documented on the eCRF.

**Note**: If subjects cannot obtain capillary blood ketone measurement, a urine ketone measurement should be obtained. Deviations from this process should be documented on the subject's diary.

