#### Collection of Information on Possible Ketone-Related Events

Information on serious and non-serious ketosis-related adverse events and related terms such as diabetic ketoacidotic hyperglycaemic coma, ketonuria, ketonaemia, ketosis, urine ketone body

present, acidosis, metabolic acidosis, blood ketone body present, blood ketone body increased will be collected on a separate eCRF and also recorded on the adverse event eCRF. If a ketosis-related adverse event meets the criteria used to define a serious adverse event (SAE), the event must be captured as an SAE on the Adverse Event eCRF.

Subjects will be asked to collect capillary blood ketones during periods of increased risk of ketonemia and to document these in a subject diary. Detailed information of episodes of elevated ketone levels requiring corrective actions (eg, increase in insulin dose, study drug interruption, etc) will be collected on the subject diary which will be reviewed by study site personnel at each scheduled visit. Information on episodes of elevated ketones will be collected on a separate eCRF, and adverse events of elevated ketone levels requiring corrective actions that are considered by the investigator to be adverse events of elevated ketones should also be recorded on the adverse event eCRF.

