#### **Adverse Events**

The terms used in the eCRFs by investigators to identify adverse events will be coded using the Medical Dictionary for Regulatory Activities (MedDRA). All reported adverse events with onset during the treatment phase (ie, treatment-emergent adverse events) will be included in the analysis. Additionally, a summary of all reported adverse events (regardless of whether treatment-emergent) will also be provided.

For each adverse event, the percentage of subjects who experienced at least 1 occurrence of the given event will be summarized by treatment group. The percentage of subjects with specific treatment-emergent adverse events will be summarized by severity and relationship to study drug, as classified by the investigator, by treatment group.

Special attention will be given to those subjects who died, or who discontinued treatment due to an adverse event, or who experienced a severe or a serious adverse event (eg, summaries, listings, and narrative preparation may be provided, as appropriate).

Further analyses, to be described in the SAP for this study, will be conducted on the pre-specified adverse events for which additional information is collected from the investigators (refer to Section 9.8, Safety Evaluations), and on other adverse events.

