6.1.1. Selected Adverse Events for Additional Analysis

To support the additional assessment of particular categories of AEs, such as vulvovaginal candidiasis, balanitis or balanoposthitis, urinary tract infections (UTIs), volume depletion, hepatic injury, renal impairment/renal failure, hypersensitivity, venous thromboembolic event, photosensitivity, and malignancy, groupings of selected preferred terms will be created. A blinded review prior to database lock will be performed to assure that no reported term suggestive of the AE of interest is omitted. The list of preferred terms that are to be combined for assessment of each of the pre-specified AEs is provided in Attachment 2. Given the planned sample size of the study (ie, 146 subjects overall), listings may be provided instead of summary tables for any selected AEs below that are reported with low incidence (ie, <5%).

Fracture events identified by the investigator or the sponsor for meeting the criteria pre-specified in the charter will be sent to an independent fracture adjudication committee to confirm that events were fractures, to determine fracture location (anatomic region) and type (low trauma or not). Summary of the fracture events will be based on the adjudicated events of fracture.

Diabetic ketoacidosis (DKA) identified by investigator or the sponsor for meeting the criteria prespecified in the charter will be sent to an independent DKA adjudication committee. Summary of the DKA events will be based on the adjudicated events of DKA.

Pancreatitis identified by investigator or the sponsor for meeting the criteria pre-specified in the charter will be sent to an independent pancreatitis adjudication committee. Summary of the pancreatitis events will be based on the adjudicated events of pancreatitis.

Lower extremity amputation will be recorded on a dedicated amputation case report form page. Summary of the lower extremity amputation will be based on the case report form page.

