6.2. Clinical Laboratory Tests

Laboratory data will be summarized for each type of laboratory test listed in Attachment 3. Normal reference ranges for each test will be provided. Descriptive statistics (N, mean, SD, median, and range, as well as the 95% CI for the change from baseline) will be reported for each laboratory analyte at baseline and at each scheduled time point for absolute value and for change from baseline. The descriptive statistics will be presented based on measurements on study medication, including up to a maximum of 2 days after the last dose of study medication, as well as all measurements regardless of the time of the last dose of double-blind study drug. Summaries based on both standard units (SI) and conventional units will be provided.

The percentage of subjects with specific treatment-emergent laboratory values meeting predefined limit of change (PDLC) criteria will be summarized for these laboratory analytes. The 95% CI for the percentage difference between canagliflozin compared to placebo will be provided for each PDLC criterion which have at least 4 or more subjects in any treatment group; a corresponding listing will also be provided. The criteria for PDLC values are listed in Attachment 4.

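### The SAP plans no analysis of the dedicated ketone-episode form, no pooled ketosis term group and no ketone limit, and its Week 12 ketone change is taken against a fasting baseline at a visit that does not require fasting

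*SAP*

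**What the plan says.** **Collection.** Protocol 9.8 lists ketone monitoring among the safety evaluations. Its subsection on possible ketone-related events says: "Information on episodes of elevated ketones will be collected on a separate eCRF". Section 9.2.1.2 adds that "the site will be required to report only the episodes of elevated ketone levels", meaning 0.6 mmol/L or above. Not every episode becomes an adverse event. Under section 9.2, "findings of elevated ketones considered by the investigator to be adverse events should also be reported in the adverse event eCRF". Section 9.8 also names nine ketosis-related terms, from ketonuria to metabolic acidosis, for a separate form and the adverse event eCRF. Section 12 makes DKA and related acidosis events adverse events of special interest, with a supplemental form.

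**Promise.** Protocol 11.6 (Adverse Events): "Further analyses, to be described in the SAP for this study, will be conducted on the pre-specified adverse events for which additional information is collected".

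**SAP.** Section 6.1.1: "Summary of the DKA events will be based on the adjudicated events of DKA". Attachment 2 has term groups for photosensitivity, hypersensitivity, volume depletion and others, but none for ketosis or acidosis. Attachment 4 has a bicarbonate limit and no ketone limit. No section mentions the ketone-episode eCRF.

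**Laboratory ketones.** The Time and Events Schedule has blood ketones on Day 1 and at Weeks 12, 26 and 52. Attachment 3 of the SAP includes them, and under SAP 6.2 descriptive statistics "will be reported for each laboratory analyte at baseline and at each scheduled time point for absolute value and for change from baseline". Protocol 9.1.1.2 sets out "The requirement to fast for at least 8 hours prior to clinic visits on Day 1 (Randomization Visit), Week 26, Week 52", and for the visit that starts rescue therapy. Week 12 is not on that list. For home ketone tests in the run-in, section 9.2.1.1 asks for a non-fasting state and gives its reason: "To avoid the confounding effect of overnight fasting on ketogenesis".

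**The concern.** Ketosis has a monitoring scheme, a diary, dedicated forms and two attachments in the protocol. In the SAP, the added analysis is a count of adjudicated DKA. If that count is close to certain to be zero, the data most likely to show a difference between arms are the milder ones: home episodes and ketosis events short of DKA. The first have no planned summary. The second are planned only as separate preferred terms.

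The SAP sets its own standard here. Hypoglycemia is collected in the same way: a diary, a dedicated eCRF, and an adverse event only if the investigator so judges. SAP 6.1.2 analyses that eCRF directly, by glucose threshold, by rate per person-year and by insulin background. The documents give no reason for treating ketones differently.

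The Week 12 laboratory change is a smaller matter. It is the only laboratory ketone change before up-titration, and its baseline was taken under a different fasting rule.

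**Working it through.** **1. The plan's own figures.**
- Arm size: 66 × 1.10 = 72.6, so 73 per arm, as in SAP 1.4.
- Adult serious DKA/acidosis percentages (Protocol 1.1.3): 4/5,337 = 0.075%, 6/5,350 = 0.112%, 2/6,909 = 0.029%. These agree with the printed 0.07%, 0.11% and 0.03%.

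**2. Expected DKA/acidosis events.** Expected = rate × subject-years; P(none) = exp(−expected). With 73 subjects followed for one year:

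| Adult rate per 100 subject-years | Expected events | P(none) |
|---|---|---|
| 0.0522 (100 mg) | 73 × 0.000522 = 0.038 | 0.963 |
| 0.0763 (300 mg) | 73 × 0.000763 = 0.056 | 0.946 |
| 0.0238 (comparator, placebo arm) | 73 × 0.000238 = 0.017 | 0.983 |

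At ten times the canagliflozin rates (an assumption), 0.38 to 0.56 events are expected. The chance of at least one is then 1 − exp(−0.38) = 32% to 1 − exp(−0.56) = 43%.

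**3. What lies below DKA.** Protocol 3.2 reports an adult canagliflozin study in which 22 of 1,297 subjects reached total ketone bodies of 3.0 mmol/L or more and none developed DKA. At that rate, 73 × 22/1,297 = 1.2 subjects are expected here, and P(at least one) = 1 − (1 − 0.01696)^73 = 71%. This is only a guide. It concerns adults and total ketones, while the home meter reads 3β-OH butyrate, which Protocol 9.2 puts at about 75% of ketones.

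**4. Precision of an episode table.** The documents give no rate for 0.6 mmol/L or more. Assuming 5% to 30% of canagliflozin subjects gives 3.7 to 21.9 subjects. The 95% half-width for a difference is 1.96 × √[p1(1−p1)/73 + p0(1−p0)/73]:
- 5% vs 2%: 5.9 points
- 20% vs 10%: 11.5 points
- 30% vs 10%: 12.6 points

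Of these three, only the last would exclude zero at the assumed values.

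**5. Preferred-term tables.** SAP 6.1 gives a confidence interval only for an adverse event reported by at least 4 subjects in an arm. Nine terms with three subjects each, up to 9 × 3 = 27 subjects, would produce no interval.

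**6. Week 12.** Let f be the fasting increment in laboratory ketones, q the share of Week 12 samples taken unfasted, and d the drug effect. With an additive increment:
- canagliflozin change = d − qf
- placebo change = −qf
- difference = d

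Illustration with assumed f = 0.10 and d = 0.07 mmol/L:
- q = 1: −0.03 and −0.10, difference 0.07.
- q = 0.5: 0.02 and −0.05, difference 0.07.

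Over an assumed f of 0.05 to 0.20 with q = 1, the within-arm shift is −0.05 to −0.20 mmol/L. At Weeks 26 and 52 both samples are fasting, so the shift is zero.

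**The case against.** **Ketosis is covered elsewhere.** A reader might infer that ketosis safety rests wholly on DKA counts and a biased laboratory change, or that events short of DKA would go unreported. The documents do not support that. Protocol 9.8 sends ketosis-related adverse events to the adverse event eCRF, and SAP 6.1 tabulates every treatment-emergent event by preferred term, severity, relationship, action taken and outcome, with listings of serious events. Attachment 4 has bicarbonate below 16 mEq/L, and Attachment 3 includes dipstick ketones and blood ketones. This stands, and it limits the point. It does not reach episodes the investigator does not call adverse events, and it does not pool the nine terms.

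**Week 12 is not shown to be a fed visit.** This also stands. Fasting is not required, which differs from being prohibited. Study drug is withheld until after this trough-sampling visit and taken before the next meal, so some subjects may attend unfed. The protocol's remark about fasting concerns home capillary tests, and no size is given for the laboratory assay.

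**The comparison between arms is safe.** A reader might infer that canagliflozin minus placebo is biased downward. With a common additive shift it is not. One qualification remains. Protocol 3.2 expects mild ketonemia especially with fasting, so a drug effect that is larger in the fasted state could look smaller at Week 12 than at Weeks 26 and 52.

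**Episode counts are soft.** After the run-in, home testing is prompted by illness or another trigger, and sites enter only elevated readings. Rates therefore mix ketosis with testing frequency. That is a reason to label the table, not to omit it.

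**The DKA rates are a rough guide.** They are adult and serious-only, and adjudication is not limited to serious events. The figures show that a DKA count is a weak basis. They do not measure what the missing table would show.

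**Conclusion.** The gap is real and should be closed before database lock. Followed as written, the SAP leaves ketone episodes not judged adverse events without any summary, spreads ketosis adverse events over separate preferred terms, and has no ketone limit. The protocol promises further SAP analyses of events with additional data collection, and the SAP gives the parallel hypoglycemia form a full analysis.

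Adjudicated DKA will very probably be uninformative: 0.04 to 0.06 expected events on canagliflozin, with a 95% to 96% chance of none. This assumes adult serious-event rates apply to children and that all 73 subjects contribute a full year.

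The Week 12 problem is confined to the within-arm change from baseline. Fasting state there is uncontrolled, and the size of the shift cannot be derived from the documents. The documents do not support a claim of bias between arms, and Weeks 26 and 52 are unaffected.

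**What to change.** Add a short ketone section to the SAP:

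1. **Ketone-episode eCRF.** By arm and by insulin background, report the number and percentage of subjects with at least one episode, and episode rates per subject-year on drug, at ≥0.6, >1.0 and >3.0 mmol/L (values already in Protocol 3.2). State beneath the table that home testing is trigger-based and that the number of tests is not entered on that form, so rates depend on testing frequency.
2. **Pooled term group.** Add a ketosis/acidosis group to Attachment 2 from the nine terms in Protocol 9.8, and tabulate it beside adjudicated DKA.
3. **Laboratory ketones.** Report change from baseline only at Weeks 26 and 52. At Week 12, use the absolute values that SAP 6.2 already plans, compared between arms, with a note that fasting was not required.

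The cost is SAP wording and about three tables. No new data are needed, and no clinical rule changes. The results remain descriptive, in line with the SAP's decision not to test safety hypotheses.

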6.1.2. Hypoglycemia

Hypoglycemia episodes are collected by a specific, dedicated eCRF. Investigators are also asked to report episodes of hypoglycemia as an adverse event if they evaluate the episode as such. Analyses discussed below are based upon events reported through the hypoglycemia eCRF. Note that reconciliation will be performed to assure that all events reported as AEs are also recorded on the hypoglycemia eCRF.

A subject will be counted as having a documented hypoglycemia episode when there is either a biochemically confirmed hypoglycemic episode (ie, concurrent fingerstick glucose or plasma glucose \leq 70 mg/dL [3.9 mmol/L]), and/or a severe hypoglycemic episode, as reported on the hypoglycemia eCRF, as follows:

- Biochemically documented hypoglycemia episode: a hypoglycemia episode with a concurrent reported glucose value of \leq 70 mg/dL (3.9 mmol/L), regardless of whether the episode is associated with symptoms (symptomatic hypoglycemia) or not (asymptomatic hypoglycemia)
- Severe hypoglycemia episode: a hypoglycemia episode that has
 - the answer "Yes" for "Convulsions/Seizure" or "Loss of consciousness/Coma" to the question "Any signs/symptoms present?", or
 - check "Subject was not Capable of Treating Self and Required Assistance" to the question "If treatment given indicate assistance needed."

Only treatment-emergent hypoglycemia episodes, reported on the eCRF for hypoglycemia, will be summarized. Treatment-emergent is defined the same way as treatment-emergent AEs (defined in Section 6.1). Given the potential confounding of rescue medication to the treatment effect, treatment-emergent hypoglycemia episodes before the initiation of rescue therapy will also be summarized.

Because the background AHA may affect the risk of hypoglycemia, treatment-emergent hypoglycemia episodes will be summarized for both 26-week core double-blind treatment period and 52-week double-blind treatment phase by the following background AHA groups at randomization before the initiation of rescue therapy and regardless of rescue therapy.

- Diet and exercise only; or metformin monotherapy.
- On insulin (with or without metformin).

The percentage of subjects with documented hypoglycemia episodes (ie, biochemically documented and/or severe) and subjects with biochemically documented, and with severe hypoglycemia episodes separately, will be summarized by treatment group. For subjects with biochemically documented hypoglycemia episodes, the percentage of subjects will be summarized for each of the following glucose levels (\leq 70 mg/dL [3.9 mmol/L], <56 mg/dL [3.1 mmol/L], and <36 mg/dL [2.0 mmol/L], "Low" results will be included in all three categories) by treatment group. For subjects with severe hypoglycemia episodes, the percentage of subjects by each answer of the 2 questions for severe hypoglycemia on the eCRF will be summarized by treatment group. Event rate by person-year (total number of episodes/total exposure) will be calculated by treatment group separately for documented and for severe hypoglycemia.

Subjects who had 0, 1, 2, or \geq 3 documented episodes and subjects who had 0, 1, 2, or \geq 3 severe hypoglycemic episodes will be summarized by treatment group.

In addition, the incidence of all episodes of hypoglycemia reported on the eCRF for hypoglycemia will be summarized (this includes events without concurrent fingerstick glucose reported and events with fingerstick glucose >70 mg/dL [3.9 mmol/L]) by treatment group.

6.2. Clinical Laboratory Tests

Laboratory data will be summarized for each type of laboratory test listed in Attachment 3. Normal reference ranges for each test will be provided. Descriptive statistics (N, mean, SD, median, and range, as well as the 95% CI for the change from baseline) will be reported for each laboratory analyte at baseline and at each scheduled time point for absolute value and for change from baseline. The descriptive statistics will be presented based on measurements on study medication, including up to a maximum of 2 days after the last dose of study medication, as well as all measurements regardless of the time of the last dose of double-blind study drug. Summaries based on both standard units (SI) and conventional units will be provided.

The percentage of subjects with specific treatment-emergent laboratory values meeting predefined limit of change (PDLC) criteria will be summarized for these laboratory analytes. The 95% CI for the percentage difference between canagliflozin compared to placebo will be provided for each PDLC criterion which have at least 4 or more subjects in any treatment group; a corresponding listing will also be provided. The criteria for PDLC values are listed in Attachment 4.

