# 11.5. Biomarker Analyses

Changes in serum osteocalcin and serum collagen type 1 CTx over time will be summarized by treatment group. Associations between baseline levels and changes from baseline in select markers and clinical response at 26 and 52 weeks of treatment will be explored. Biomarker analyses will be summarized in separate technical reports.

Biomarker results will be presented in a separate report.

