1.1. Trial Objectives

In children and adolescents (≥ 10 to <18 years) with type 2 diabetes mellitus (T2DM) who have inadequate glycemic control (ie, hemoglobin A_{1c} [HbA_{1c}] of $\geq 6.5\%$ to $\leq 10.5\%$), either on diet and exercise only, or on diet and exercise and metformin monotherapy, or on diet and exercise and insulin monotherapy with metformin and insulin.

Primary Objectives

- To assess the effect of canagliflozin relative to placebo on HbA_{1c} after 26 weeks of treatment.
- To assess the overall safety and tolerability of canagliflozin.

Major Secondary Objectives

- After 26 weeks of treatment, to assess the effect of canagliflozin relative to placebo on HbA_{1c} in the subset of subjects on a background of metformin (with or without insulin).
- After 26 weeks of treatment, to assess the effect of canagliflozin relative to placebo on HbA_{1c} in the subset of subjects on a background of diet and exercise only.
- After 26 weeks of treatment, to assess the effect of canagliflozin relative to placebo on:
 - Fasting plasma glucose (FPG).
 - Proportion of subjects with $HbA_{1c} < 7.5\%$, < 7.0%, and < 6.5%.
 - Time to rescue therapy and proportion of subjects receiving rescue therapy.
 - Body weight.
- After 52 weeks of treatment, to assess the effect of canagliflozin relative to placebo on:
 - HbA_{1c} and FPG.
 - Proportion of subjects with $HbA_{1c} < 7.5\%$, <7.0%, and <6.5%.
 - Time to rescue therapy and proportion of subjects receiving rescue therapy.
 - Body weight.

Additional Secondary Objectives

- After 12 weeks of treatment to assess the effects of canagliflozin relative to placebo on HbA_{1c}.
- After 26 weeks of treatment, to assess the effect of canagliflozin 100 mg relative to placebo on HbA_{1c}.
- After 26 weeks of treatment, to assess the effect of canagliflozin 100 mg followed by a dose increase to 300 mg relative to placebo on HbA_{1c}.

- After 26 weeks and 52 weeks of treatment, to assess the effect of canagliflozin relative to placebo on:
 - Body mass index (BMI).
 - Fasting plasma lipids (ie, low-density lipoprotein-cholesterol [LDL-C], high-density lipoprotein-cholesterol [HDL-C], total cholesterol, non-HDL-C, LDL-C to HDL-C ratio, non-HDL-C to LDL-C ratio, and triglycerides).
 - Systolic blood pressure (SBP) and diastolic blood pressure (DBP).
 - Growth velocity and Tanner Staging.

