 - Markers of calcium and phosphate homeostasis, (calcium, magnesium, phosphate, parathyroid hormone [PTH], 25-hydroxy Vitamin D, calcitonin; urinary excretion of calcium and phosphate).
 - Bone turnover markers (serum osteocalcin and serum collagen type 1 carboxy-telopeptide [CTx]).
 - Urinary albumin/creatinine ratio (ACR).

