Central laboratory will report the estimated glomerular filtration rate (eGFR) at study visits when serum creatinine is measured as specified below:

- Estimated Glomerular Filtration Rate (eGFR)
 - eGFR will be calculated using Schwartz formula:
 - eGFR $(mL/min/1.73 \text{ m}^2) = (0.55 \times \text{height in cm}) / \text{serum creatinine in mg/dL for}$ girls from 10 to <18 years of age and boys from 10 to 12 years of age
 - $\circ~$ eGFR (mL/min/1.73 m²) = (0.70 \times height in cm) / serum creatinine in mg/dL for boys from 13 to <18 years of age

Laboratory Test	Parameter for ANY value and LAST value		
Chemistry			
	Absolute Value: >3X ULN		
ALT	Absolute Value: >5X ULN		
	Absolute Value: >8X ULN		
	Absolute Value: >3X ULN		
AST	Absolute Value: >5X ULN		
	Absolute Value: >8X ULN		
ALT >3X ULN and Tbili >2X	Composite: ALT >3X ULN and Tbili >2X ULN [with the Tbili elevation		
ULN	>2 X ULN within 30 days of the ALT elevation >3x ULN]		
AST >3X ULN and Tbili >2X	Composite: AST >3X ULN and Tbili >2X ULN [with the Tbili elevation		
ULN	>2 X ULN within 30 days of the AST elevation >3x ULN]		
Bilirubin	Composite: >ULN and >25% increase from BL		
	Absolute Value: >2X ULN		
Bicarbonate	Absolute Value: <16 mEq/L		
Calcium	Composite: >ULN and >10% increase from BL		
Magnesium	Composite: >ULN and >25% increase from BL		
Phosphorus Composite: >ULN and >25% increase from BL			
Potassium	Composite: <lln and="">15% decrease from BL</lln>		
	Composite: >ULN and >15% increase from BL		
	Absolute Value: $\geq 6.5 \text{ mEq/L}$		
Sodium	Composite: <lln and="" decrease="">5 mEq/L or more from BL</lln>		
	Composite: >ULN and increase>5 mEq/L or more from BL		
Urate	Composite: <lln and="">25% decrease from BL</lln>		
Hematology			
Hemoglobin	Change: $\geq 2 \text{ g/dL}$ decrease from BL		
	Change: $\geq 2 \text{ g/dL}$ increase from BL		
Vital signs			
Pulse	Absolute Value: ≤50 beats per minute		
	Absolute Value: ≥ 100 beats per minute		
Systolic Blood Pressure	Composite: ≥20 mm Hg decrease from BL and ≤90 mm Hg		
	Composite: ≥ 20 mm Hg increase from BL and ≥ 160 mm Hg		
Diastolic Blood Pressure	Composite: ≥ 15 mm Hg decrease from BL and ≤ 50 mm Hg		
	Composite: ≥15 mm Hg increase from BL and ≥100 mm Hg		

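### No between-arm difference in mean change is pre-specified for the bone-turnover markers, calcium/phosphate markers or urinary ACR, although the objective is to assess them relative to placebo

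*SAP*

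**What the plan says.** SAP 1.1, like Protocol 2.1, words the objective as a contrast: "After 26 weeks and 52 weeks of treatment, to assess the effect of canagliflozin relative to placebo on" a list that includes BMI, fasting lipids, blood pressure, calcium/phosphate markers, osteocalcin and CTx, and urinary ACR.

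BMI, lipids and blood pressure reappear among the secondary endpoints (Protocol 11.3.3, SAP 5.3.1), and lipids and blood pressure again in SAP 5.4.1. The bone, calcium/phosphate and ACR measures appear in none of these lists. They enter the analysis through Attachment 3 and SAP 6.2, where "Descriptive statistics (N, mean, SD, median, and range, as well as the 95% CI for the change from baseline) will be reported" for each analyte at baseline and each scheduled visit.

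The next paragraph of SAP 6.2 adds a between-arm element: "The 95% CI for the percentage difference between canagliflozin compared to placebo will be provided for each PDLC criterion", provided at least four subjects in any group meet it. Attachment 4 has criteria for calcium ("Composite: >ULN and >10% increase from BL"), magnesium and phosphorus.

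Protocol 11.5 says "Changes in serum osteocalcin and serum collagen type 1 CTx over time will be summarized by treatment group" and sends biomarker results to a separate report. Protocol 11.6 lists change from baseline for the bone and calcium/phosphate markers. SAP 6 rules out imputation of laboratory values and hypothesis testing for safety results.

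**The concern.** The objective asks for an effect relative to placebo, while the specified analysis describes change within each arm. In subjects aged 10 to under 18, whose growth velocity and Tanner stage are being followed, change within the canagliflozin arm mixes any drug effect with whatever would have happened anyway. Protocol 3.2 gives separating those two as the reason for having a placebo arm.

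The bone question is live in the sponsor's own background. Protocol 1.1.3 reports modest increases in CTx and osteocalcin in adults, placebo-adjusted total-hip BMD changes of -0.9% and -1.2%, and fracture rates of 1.6, 1.6 and 1.1 per 100 subject-years (100 mg, 300 mg, placebo) in the cardiovascular study. The same section reports minimal BMD change at the other three sites and no fracture difference in about 5,800 other adults, so the question is open in both directions.

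Bone and calcium/phosphate samples take 30 + 30 = 60 mL of the estimated 173 mL of blood per subject (Protocol Table 3), about 35%. Data collected at that burden should go into the comparison the objective names.

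**Working it through.** **1. Trace of each objective item to its planned analysis.**

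| Item | Between-arm comparison of change | Between-arm CI for PDLC percentage |
|---|---|---|
| Lipids | ANCOVA at Weeks 26 and 52; Wilcoxon and Hodges-Lehmann for triglycerides (SAP 5.4.2) | none |
| BMI, blood pressure | MMRM (SAP 5.3.2; blood pressure also 5.4.2) | none |
| Calcium, magnesium, phosphate | none | yes, high values only, if at least 4 subjects in a group |
| PTH, 25-hydroxy vitamin D, calcitonin, urinary calcium, urinary phosphate | none | none |
| Osteocalcin, CTx | none | none |
| Urinary ACR | none | none |

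The last four rows hold 3 + 5 + 2 + 1 = 11 measures. None has a planned difference in mean change. Three have a conditional difference in percentages, and 11 - 3 = 8 have no between-arm estimate. The condition of four subjects is 4/73 = 5.5% of a randomised arm. It concerns excursions above the upper limit of normal, so it does not see a shift in the mean within the normal range or downwards.

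Lipids are sampled at baseline, Week 26 and Week 52 (SAP 5.4.2), and the bone and calcium/phosphate markers share that schedule (Protocol 9.7). ACR differs only in taking its baseline at Week -2. The SAP therefore already contains a model form that fits.

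**2. What a reader could recover from the planned tables.** With N, mean and SD of change in each arm, the unadjusted difference is D = m_C - m_P, with SE = sqrt(s_C²/n_C + s_P²/n_P). The interval D ± t × SE follows directly.

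A baseline-adjusted difference is D - b × (baseline mean_C - baseline mean_P), where b is the pooled within-arm slope of change on baseline. Neither b nor the breakdown by AHA background and age group is in the planned summaries, so this estimate and its standard error cannot be rebuilt. The gain in precision depends on the within-arm correlation of change with baseline, which the documents do not give.

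**3. Scale, in SDs of change (illustrative).** The documents give no marker SDs, so I use SD units, equal SDs and the plan's 66 evaluable subjects per arm. That figure reproduces: the average effect is 0.5 × 0.5 + 0.25 × 0.4 + 0.25 × 0.5 = 0.475, and with SD 0.9, two-sided 0.05 and a t-test, 66 per arm gives 85.3% power. It is the HbA1c Week 26 number, not a count for these markers.

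- Direct 95% CI for the difference, half-width: 1.96 × sqrt(2/66) = 0.34 SD.
- Each within-arm 95% CI, half-width: 1.96/sqrt(66) = 0.24 SD.
- Difference needed for those two intervals not to overlap: 2 × 1.96/sqrt(66) = 0.48 SD, which is sqrt(2) = 1.41 times as large.
- Two-sided level implied by non-overlap: 2 × (1 - Φ(2 × 1.96/sqrt(2))) = 0.006.

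These figures show only what is lost if someone compares the two printed intervals by eye.

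**The case against.** The strongest reply is that these are safety measures. Protocol 9.8 lists them as such, SAP 6 plans no safety testing, and descriptive reporting by arm suits a low-tier objective. That classification stands, but it does not rule out an estimate with an interval: SAP 6.1 and 6.2 already give between-arm 95% CIs for adverse-event and PDLC percentages without testing.

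A reader might infer that the SAP offers no between-arm estimate at all for these markers. It does not go that far, because the PDLC provision covers calcium, magnesium and phosphorus. A reader might also infer that the objective cannot be answered, or that two separate intervals are all there is to compare. That is too strong as well. N, mean and SD are planned, the bone markers are to be summarised by treatment group, and the unadjusted difference follows.

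Nor does any passage make non-overlap of intervals a decision rule. The factor of 1.41 holds in any trial with equal arms, so it cannot be read as a loss that this plan incurs.

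Protocol 11.5 promises a separate biomarker report. It is not among the documents, so it may contain such a comparison, but it cannot count as pre-specification here. Fractures are also adjudicated independently (SAP 6.1.1), so bone safety does not rest on markers alone.

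On ACR, the median and range are planned beside the mean and SD, which partly meets the worry about outliers. No between-arm interval accompanies the median. Subjects with proteinuria can be enrolled (Protocol 9.8), so a skewed distribution is plausible. For CTx, osteocalcin and PTH the documents say nothing about distribution, so there is no basis for requiring a log scale in advance.

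**Conclusion.** The point holds in a limited form. For all 11 measures the plan lacks a pre-specified between-arm difference in mean change, and for eight of them the SAP plans no between-arm estimate of any kind. This is a mismatch between a stated objective and its analysis. It is no threat to the primary result, and it does not mean the data cannot answer the question.

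What would be lost is the adjusted estimate and its pre-specification, since the crude difference can be derived afterwards. The size of the gain from adjustment cannot be computed from the documents. The 0.48 against 0.34 SD comparison is illustrative and assumes equal SDs and 66 per arm. The conclusion on the eight measures rests on the SAP and protocol as they stand and leaves open what the separate biomarker report may hold.

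**What to change.** In SAP 6.2, for each of the 11 measures, add the canagliflozin-minus-placebo difference in change from baseline with a 95% CI at Weeks 26 and 52. Use an ANCOVA with treatment, AHA background, age group and baseline value, which is the model form SAP 5.4.2 uses for lipids. Fit it to observed values without imputation, in keeping with SAP 6 (so without the LOCF applied to lipids), and on the safety analysis set. State whether it uses on-treatment measurements, all measurements, or both, since SAP 6.2 presents both.

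For urinary ACR, use a method suited to skewed data. This can be the Hodges-Lehmann estimate and interval already planned for triglycerides, or a log-scale ANCOVA reported as a ratio. Extend this to other markers only if they prove skewed.

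Present all of these as estimates without hypothesis tests. The testing sequence is untouched and no new samples are needed. The cost is a paragraph in the SAP and a few extra tables. If the sponsor does not want the comparison, the lesser remedy is to reword the objective as descriptive.
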